4.4.3 Handling of Missing Values/Censoring/Discontinuations

Missing data will not be replaced or imputed. Dropouts will be included in analyses up to the point of discontinuation.

4.5 Analysis of Secondary Objectives

All secondary analyses will be conducted only on MITT population.

No alpha adjustments will be made for multiple secondary endpoints due to the exploratory nature of the inferences. All statistical tests of hypothesis will be similar to that mentioned for primary analysis and will be two-sided with 0.05 level of significance.

4.5.1 Efficacy (Secondary)

The analysis of each secondary endpoint is as follows:

Change from baseline in TEWL (legs) at Day 29

For TEWL (legs) endpoint, the comparison will be performed on area 5 and area 6.

The summary ([Table 14.2.2.2.1](#)) and statistical analysis ([Table 14.2.2.2.2](#)) of this endpoint will be performed in a similar fashion to the primary analysis.

The TEWL (legs) measurements at Day 29 will be listed in [Listing 16.2.6.1](#).

Change from baseline in TEWL (face and legs) at Day 15

The summary ([Table 14.2.2.1.1.1](#) for face and [Table 14.2.2.2.1](#) for legs) and statistical analysis ([Table 14.2.2.1.1.2](#) for face and [Table 14.2.2.2.2](#) for legs) of this endpoint will be performed in a similar fashion to the primary analysis.

The TEWL (face and legs) measurements at Day 15 will be listed in [Listing 16.2.6.1](#).

Change from baseline in Corneometer measurement (face and legs) at Day 1: 30 minutes, 6 hours, and Day 2: 24 hours after the first supervised application

The summary ([Table 14.2.3.1.1](#) for face and [Table 14.2.3.2.1](#) for legs) and statistical analysis ([Table 14.2.3.1.2](#) for face and [Table 14.2.3.2.2](#) for legs) of these endpoints will be performed in a similar fashion to the primary analysis.

The percentage difference between each test product + standard cleanser soap and standard cleanser soap (only) for Corneometer measurements will be presented at each timepoint. The percentage difference will be obtained using following formulae:

$100 * [\text{Adjusted mean difference in each test product + standard cleanser soap and standard cleanser soap (only)}] / \text{Adjusted Mean of Corneometer measurements for standard cleanser soap (only)}$.

The denominator of above formulae will be obtained by mixed model ANCOVA with absolute value as response variable and baseline Corneometer measurements as covariate. This model will be fitted for standard cleanser soap (only).

The plot ([Figure 14.2.2.1.1](#) for face and [Figure 14.2.2.1.2](#) for legs) of mean Corneometer measurements will be presented with various timepoints (30 minutes, 6 hours, and 24 hours) of Day 1 on x-axis and corresponding mean value on y-axis. Separate colour codes will be used for each treatment arm. The post baseline timepoints, with statistically significant p-value of mean difference between each test product + standard cleanser soap and standard cleanser soap (only) obtained from ANCOVA model defined in primary analysis section will be indicated in this plot.

The listing of Corneometer measurements at various timepoints on Day 1 and Day 2 will be listed in [Listing 16.2.6.2](#) for all randomized subjects.

Change from baseline in Corneometer measurements (face and legs) at Day 15 and Day 29

The summary ([Table 14.2.3.1.1](#) for face and [Table 14.2.3.2.1](#) for legs) and statistical analysis ([Table 14.2.3.1.2](#) for face and [Table 14.2.3.2.2](#) for legs) of these endpoints will be performed in a similar fashion to the primary analysis.

The percentage difference between each test product + standard cleanser soap and standard cleanser soap (only) for Corneometer measurements will be presented at each visit. The percentage difference will be obtained using following formulae:

$100 * [\text{Adjusted mean difference in each test product + standard cleanser soap and standard cleanser soap (only)}] / \text{Adjusted Mean of Corneometer measurements for standard cleanser soap (only)}$.

The denominator of above formulae will be obtained by mixed model ANCOVA with absolute value as response variable and baseline Corneometer measurements as covariate. This model will be fitted for standard cleanser soap (only).

The plot ([Figure 14.2.2.2.1](#) for face and [Figure 14.2.2.2.2](#) for legs) of mean Corneometer measurements will be presented with visits on x-axis and the mean value on y-axis. Separate colour codes will be used for each treatment arm. This plot will include all the visits from baseline until Visit 10 (Day 34). The post baseline visits, with statistically significant p-value of mean change from baseline difference between each study product + standard cleanser soap and standard cleanser soap (only) obtained from ANCOVA model defined above will be indicated in this plot.

The listing of Corneometer measurements at Day 15 and Day 29 will be listed in [Listing 16.2.6.2](#) for all randomized subjects.

Change from baseline in TEWL (face and legs) at Day 30, 31, 32, 33, and 34

The summary ([Table 14.2.4.1.1](#) for face and [Table 14.2.4.2.1](#) for legs) and statistical analysis ([Table 14.2.4.1.2](#) for face and [Table 14.2.4.2.2](#) for legs) of this endpoint will be performed in a similar fashion to the primary analysis.

The TEWL (face and legs) measurements at Day 30, 31, 32, 33, and 34 will be listed in [Listing 16.2.6.1](#).

Change from baseline in Corneometer measurements (face and legs) at Day 30, 31, 32, 33, and 34

The summary ([Table 14.2.5.1.1](#) for face and [Table 14.2.5.2.1](#) for legs) and statistical analysis ([Table 14.2.5.1.2](#) for face and [Table 14.2.5.2.2](#) for legs) of this endpoint will be performed in a similar fashion to the primary analysis. The analysis will be performed separately at each visit.

The listing of Corneometer measurements at Day 30, 31, 32, 33, and 34 will be listed in [Listing 16.2.6.2](#) for all randomized subjects.

Change from pre-challenge TEWL (face and legs) at Day 29

The change in TEWL values from pre- to post D-Squame challenge on Day 29 will be summarized descriptively ([Table 14.2.6.1.1](#) for face and [Table 14.2.6.2.1](#) for legs) and statistically analyzed ([Table 14.2.6.1.2](#) for face and [Table 14.2.6.2.2](#) for legs) similar to the primary analysis, with baseline value as the pre- D-Squame value. Summarization and analyses will be for values after 3, 6, and 9 discs removed from the face and 4, 8, and 12 discs removed from the legs.

The percentage difference between each test product + standard cleanser soap and standard cleanser soap (only) for TEWL value will be presented at removal of 3, 6 and 9 discs. The percentage difference will be obtained using following formulae:

$100 * [\text{Adjusted mean difference in each test product + standard cleanser soap and standard cleanser soap (only)}] / \text{Adjusted Mean of TEWL value for standard cleanser soap (only)}$.

The denominator of above formulae will be obtained by mixed model ANCOVA with absolute value as response variable and pre- D-Squame TEWL value as covariate. This model will be fitted for standard cleanser soap (only).

The listing of pre-challenge and post-challenge TEWL measurements at Day 29 will be listed in [Listing 16.2.6.3.1](#) for face and [Listing 16.2.6.3.2](#) for legs for all randomized subjects.

Total protein content

The protein content of each D-Squame disc and the total value of all the discs together (area 3 and 4 on the face and area 7 and 8 on the legs) will be summarized descriptively (n, mean, SD, SE, median, minimum, and maximum) by treatment arm ([Table 14.2.7.1.1](#) for face and [Table 14.2.7.2.1](#) for legs).

The total protein content ([Table 14.2.7.1.2](#) for face and [Table 14.2.7.2.2](#) for legs) will be analysed by mixed model analysis of variance (ANOVA) with observed value as a response variable, treatment arm and side of the face or leg (right, left) as factors. Subject will be included as a random effect.

The adjusted mean for each treatment arm will be presented along with SE, 95% Confidence Interval (CI) for the adjusted mean, and p-value. Also, the adjusted mean difference between each test product + standard cleanser soap and standard cleanser soap (only) along with SE, 95% CI of the difference from standard cleanser soap, and p-value will be presented.

The assumptions underlying ANOVA analysis will be checked and in case of any deviation from them, an appropriate transformation to the data will be performed to facilitate the above method of analysis. In the absence of an appropriate data transformation, non-parametric analyses will be performed. In the case of a non-parametric analysis, median differences will be presented, together with 95% CIs based on the Hodges-Lehmann method.

The percentage difference between each test product + standard cleanser soap and standard cleanser soap (only) for total protein content will be presented. The percentage difference will be obtained using following formulae:

$100 * [\text{Adjusted mean difference in each test product} + \text{standard cleanser soap and standard cleanser soap (only)}] / \text{Adjusted Mean of total protein content for standard cleanser soap (only)}$.

The denominator of above formulae will be obtained by mixed model ANCOVA with absolute value as response variable and baseline total protein content as covariate. This model will be fitted for standard cleanser soap (only).

The listing ([Listing 16.2.6.4.1](#) for face and [Listing 16.2.6.4.2](#) for legs) of protein measurement at Day 29 or any other unscheduled visits will be presented for all randomized subjects.

4.6 Analysis of Safety

All safety data will be reported for the safety population as per the actual treatment received. The safety profile of the study treatment will be assessed with respect to adverse events (AEs).

4.6.1 Adverse Events and Serious Adverse Events

All AEs will be reviewed by the Clinical Research Scientist or Designee prior to database lock and will be coded to a system organ class (SOC) and preferred term (PT) using the Medical Dictionary for Regulatory Activities (MedDRA). During this review stage, AEs will be further categorized as skin or non-skin.

Treatment emergent adverse events (TEAEs) are defined as new AEs that occur on or after the first treatment application (if this date is missing a suitable alternative will be used e.g., date of randomization). AEs with an onset date/time prior to the first treatment application will be considered as non-treatment emergent.

Summary of the number and percentage of subjects with at least one AE, total number of AEs, number and percentage of AEs within each SOC and PT will be displayed.

The treatment-related AE tables will be summarized by treatment arms (test product 1 + standard cleanser soap, test product 2 + standard cleanser soap, and standard cleanser soap alone); whereas, all other AE tables will be summarized by treatment regimen.

The listing of AEs will be provided by treatment regimen.

The following summary tables and listings will be presented by test product.

- Table of TEAEs by SOC and PT ([Table 14.3.1.1.1](#)).
- Table of TEAEs by Skin or Eye/Non-Skin or Non-Eye and PT ([Table 14.3.1.1.2](#))
- Table of TEAEs by SOC, PT, and severity ([Table 14.3.1.1.3](#))
- Table of treatment-related TEAEs by SOC and PT ([Table 14.3.1.2.1](#))
- Table of treatment-related TEAEs by Skin or Eye/Non-Skin or Non-Eye and PT ([Table 14.3.1.2.2](#))
- Table of treatment-related TEAEs by SOC, PT, and severity ([Table 14.3.1.2.3](#))

-
- Table of treatment-emergent serious adverse events (SAEs) by SOC and PT ([Table 14.3.1.3](#)) [only produced if there are more than 5 SAEs]
 - Table of treatment-emergent non-serious AEs by SOC and PT ([Table 14.3.1.4](#)) [only produced if there are more than 5 SAEs]
 - Table of TEAEs leading to study or treatment discontinuation by SOC and PT ([Table 14.3.1.5](#)).
 - Listing of all AEs ([Listing 16.2.7.1](#) for all randomized subjects; [Listing 16.2.7.2](#) for non-randomized subjects)
 - Listing of deaths ([Listing 14.3.2.1](#))
 - Listing of non-fatal SAEs ([Listing 14.3.2.2](#))
 - Listing of treatment-emergent AEs leading to study or treatment discontinuation ([Listing 14.3.2.3](#))
 - Listing of treatment-emergent AEs classified as skin or eye ([Listing 14.3.2.4](#))

In the event that there is nothing to report, a null table or listing will be produced.

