- Have no more than a 0.5-unit difference in total score between each side of the face;
- Have a dermatologist score of ≥ 1 (slight) for roughness for each side of the face;
- Have no scores of 4 (very severe) for tightness, dullness, scaling or roughness.

To confirm (per Appendix 1) whether subjects have very dry skin on **both their legs** at the screening visit (Visit 1) and Baseline visit (Visit 2) they will:

• Undergo dermatologist assessment of dullness, scaling and roughness on both legs (scale range 0-4 for each parameter).

The sum of the dermatologist assessment scores for each leg will be calculated. The total possible score for each leg is 12.

To be eligible to participate in this study, a subject must:

- Have a total score of ≥6 for each leg;
- Have no more than a 1-unit difference in total score between each leg;
- Have no scores of 4 (very severe) for dullness, scaling or roughness.

Subjects considered eligible to participate in the study will undergo a 5 to 7-day washout period, during which only the standard soap will be used on the face and legs as a standard cleanser. Subjects will be instructed to use the standard soap to cleanse the face and lower legs, as needed. Subjects will be provided a paper diary to complete during the washout period to record compliance with the soap use. This standard soap will also be used throughout the study.

At the baseline visit (Day1/Visit 2), after completion of the washout period, subjects who are deemed eligible to continue in the study will be randomized to one of the two treatment regimens. Baseline instrumental assessments of TEWL and skin moisturization (using a Corneometer) will be taken before prior to any test product application (moisturizer). Study staff will dispense study products and product use diary cards to subjects. First application of

Protocol Number: 209638 Draft Clinical Protocol

[figure not shown]
study product will be supervised by the study site staff. Subjects will be instructed to apply their assigned study product (moisturizer) to the designated side of the face and leg. Instrumental measurement of skin moisturization (using a Corneometer) will be performed at 30 minutes and 6 hours following the first single product application.

A total of 8 areas will be assigned to each subject:

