10 ADVERSE EVENT AND SERIOUS ADVERSE EVENTS

10.1 Definition of an Adverse Event (AE)

An AE is any untoward medical occurrence in a clinical study subject, temporally associated with the use of a study product including any washout or lead-in product (or medical device), whether or not considered related to the study product, including any washout or lead-in product (or medical device).

NOTE: An AE can therefore be any unfavorable and unintended sign (including an abnormal laboratory finding), symptom, or disease (new or exacerbated) temporally associated with the use of a study product including any washout or lead-in product (or medical device).

Events Meeting the AE Definition:

- Any abnormal laboratory test results (hematology, clinical chemistry, or urinalysis) or
 other safety assessments (e.g. ECG, radiological scans, vital sign measurements),
 including those that worsen from baseline, considered clinically significant in the
 medical and scientific judgment of the investigator (i.e., not related to progression of
 underlying disease).
- Exacerbation of a chronic or intermittent pre-existing condition including either an increase in frequency and/or intensity of the condition.
- New conditions detected or diagnosed after study product administration even though it may have been present before the start of the study.
- Signs, symptoms, or the clinical sequelae of a suspected drug-drug interaction.
- Signs, symptoms, or the clinical sequelae of a suspected overdose of either study product or a concomitant medication. Overdose per se will not be reported as an AE/SAE unless it is an intentional overdose taken with possible suicidal/self-harming intent. Such overdoses should be reported regardless of sequelae.
- "Lack of efficacy" or "failure of expected pharmacological action" per se will not be reported as an AE. Such instances will be captured in the efficacy assessments. However, the signs, symptoms, and/or clinical sequelae resulting from lack of efficacy will be reported as AE if they fulfill the definition of an AE.

Events NOT meeting the AE definition:

- Any clinically significant abnormal laboratory findings (if applicable) or other abnormal safety assessments which are associated with the underlying disease, unless judged by the investigator to be more severe than expected for the subject's condition.

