10.3 Reporting of Adverse Events

10.3.1 Reporting Period

All AEs, and therefore all SAEs will be collected immediately after a subject provides consent to participate in the study by the completion (signature) of the ICF and until 5 days following last administration of the study product (or last procedure).

Medical occurrences that began before obtaining informed consent will be recorded in the Medical History/Current Medical Conditions section of the CRF not the AE section.

Details recorded by the subject on a diary or similar document that meet the definition of an AE must also be discussed with the subjects and transcribed in the AE section of the CRF.

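### The SAP decides treatment emergence by onset date alone, so a washout-onset AE that worsens under the moisturizer can drop out of every AE summary table, depending on how the site records the worsening

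*SAP*

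**What the plan says.** SAP section 4.6.1 defines treatment emergence in two sentences. The first reads: "Treatment emergent adverse events (TEAEs) are defined as new AEs that occur on or after the first treatment application". The second deals with everything earlier: "AEs with an onset date/time prior to the first treatment application will be considered as non-treatment emergent". A bracket in the first sentence covers an unknown application date: "if this date is missing a suitable alternative will be used e.g., date of randomization". Neither sentence mentions an event that was already present and then got worse.

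No other text fills the gap. Protocol section 12.2.8 calls for summaries of treatment-emergent AEs but does not define the term. SAP Table 5-1, which lists changes from the protocol's analysis plan, covers only the per-protocol population.

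The surrounding rules in the protocol are these:

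- Section 4.1 sets a washout of 5 to 7 days, "during which only the standard soap will be used on the face and legs as a standard cleanser".
- Section 10.3.1 starts AE collection before that washout: "All AEs, and therefore all SAEs will be collected immediately after a subject provides consent to participate in the study".
- Section 10.1 covers events "temporally associated with the use of a study product including any washout or lead-in product", so a reaction to the washout soap can be an AE. Its list of events that qualify includes: "Exacerbation of a chronic or intermittent pre-existing condition including either an increase in frequency and/or intensity of the condition".
- Section 10.6 sends new or updated information on a reported event to the AE page of the CRF. It does not say whether a rise in severity is an edit to the existing entry or a fresh entry with its own onset date.

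**The concern.** The purpose of treatment emergence is to separate events that could be due to the product from those already there before it was used. A reaction that was mild on soap and becomes more severe once the moisturizer is added belongs, for its worsening, on the product side. A rule that looks only at onset puts it on the other side.

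This matters because local tolerance is the only safety objective, its endpoint is the frequency and severity of AEs, and SAP section 4.6.2 says there are no other safety variables. The subjects have dry, sensitive facial skin, and the moisturizer goes on one side only. A reaction that worsens on the moisturizer side and not on the soap side is informative about tolerance. The analysis should not lose it from its summaries because of a date rule.

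**Working it through.** No arithmetic applies. The plan states no figure on this point, and the issue is a classification rule. The check applies that rule to the case at issue.

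**Step 1: fix the cut-off.** The SAP does not say what the first treatment application is, and soap alone is itself one of the treatment arms. The fallback to the randomization date indicates that the first moisturizer application on Day 1 (Visit 2) is meant, not the first use of soap in the washout. I take it so.

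**Step 2: define the case.** The AE has onset between screening (Day -7 to Day -5) and the Day 1 application. It is still present after Day 1, and its severity increases after the first moisturizer application.

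**Step 3: apply the rule under each way of recording the worsening.**

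| How the worsening is recorded | Onset date used | SAP 4.6.1 class | Where it appears |
|---|---|---|---|
| Existing AE record updated | In the washout | Non-treatment-emergent | Listing 16.2.7.1; also Listing 14.3.2.1 or 14.3.2.2 if fatal or serious |
| New AE record opened | After the first application | Treatment-emergent | TEAE tables and listings, as applicable |

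**Step 4: see which outputs are affected in the first row.** Every AE summary table in SAP 4.6.1 is limited to treatment-emergent events:

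- Tables 14.3.1.1.1 to 14.3.1.1.3: all TEAEs, including by severity.
- Tables 14.3.1.2.1 to 14.3.1.2.3: treatment-related TEAEs.
- Tables 14.3.1.3 and 14.3.1.4: serious and non-serious events, where produced.
- Table 14.3.1.5: events leading to study or treatment discontinuation.

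Listings 14.3.2.3 (discontinuations) and 14.3.2.4 (skin or eye) carry the same limit. An event that went from mild to severe, was judged related and ended in withdrawal would be in none of these. Protocol 12.2.8 nevertheless asks for summaries of treatment-related AEs and of AEs leading to discontinuation.

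**Step 5: ask which row the documents favour.** Protocol 10.6 points to the first, since it speaks of adding updated information to the AE page. Protocol 10.1 gives some support to the second, since it treats an exacerbation as an AE. But that clause concerns a chronic or intermittent pre-existing condition, and it sets no rule for an AE already on record. The result therefore depends on a recording choice that the documents leave open.

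**Step 6: size.** The number misclassified is the number of randomized subjects with a recorded washout-onset AE that passes the Visit 2 check, persists past Day 1, then worsens, and is kept on one record. The documents give a rate for none of these steps.

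**The case against.** The strongest reply is that the protocol already handles the case. Section 10.1 counts an increase in intensity as an AE. The same section excludes day-to-day fluctuation of existing conditions only where they do not worsen, which implies that worsening is reportable in its own right. If the site enters it as a separate AE, the onset falls after the first application and the SAP wording captures it. The instruction to do so may also sit in CRF completion guidance, which is not among the documents. This stands as far as it goes. It makes the loss conditional on recording practice, but it does not show which practice applies, and section 10.6 leans towards updating the existing entry.

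Second, the exposed group is narrow. The Schedule of Activities repeats the inclusion and exclusion criteria at Visit 2, and section 5.4 requires all of them to be met for randomization. Open sores, pimples or cysts at the application site, an interfering active dermatosis and any very severe dryness score all exclude a subject. The investigator may also exclude at discretion. Sections 5.8 and 10.1 add that responses describable on the dryness scale are not usually recorded as AEs. All of this stands. It reduces the number of cases but does not correct the rule, because a milder reaction that qualifies as an AE can pass the check.

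Third, nothing is lost from the report. The all-AE listing keeps the event, and a line-by-line check is feasible with about 150 subjects at one centre. That is true, but the listing does not enter any count of frequency or severity.

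**Conclusion.** The definition has a real gap with a limited reach. Under SAP 4.6.1 as written, a washout-onset AE that persists past Day 1 and worsens after the first moisturizer application is non-treatment-emergent if the worsening is recorded as an update. It is then absent from all AE summary tables and from Listings 14.3.2.3 and 14.3.2.4, and it remains in Listing 16.2.7.1. This rests on two assumptions: that the first treatment application means the first moisturizer use on Day 1, and that the site follows protocol 10.6 by updating the existing entry.

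A reader might infer two stronger things that the documents do not support. One is that every such event is bound to be excluded. That does not follow, because a worsening entered as a new AE would count. The other is that the size can be found by applying an assumed rate of washout skin AEs to the 150 subjects; a rate of 2 to 5%, for example, gives 150 × 0.02 = 3 to 150 × 0.05 = 7.5. No such rate is in the documents. The count would also include events that resolve or stay unchanged, which are correctly non-treatment-emergent. The number affected cannot be estimated and is probably small.

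Safety reporting here is descriptive, so no hypothesis test, success criterion or efficacy result is touched. The change is still worth making, because it bears on the only safety objective and costs very little.

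**What to change.** In SAP 4.6.1, define a TEAE as an AE with onset, or with an increase in severity, on or after the first moisturizer application. Naming the moisturizer also removes the ambiguity over soap. Amend the second sentence so that an earlier-onset AE is non-treatment-emergent only if its severity does not increase from that point on.

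In the CRF instructions, tell the site to record such an increase either as a new AE entry with its own onset date or as a dated severity change on the existing entry. One method should be chosen and used throughout, so that the rule can be programmed. If the CRF guidance already requires a new entry, the SAP need only refer to it and state that such entries count as TEAEs.

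The cost is about one sentence in the SAP and one in the CRF guidance. Design, sample size and efficacy analyses do not change. A few more events may count as TEAEs, which is the cautious direction for a tolerance conclusion.

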To evaluate the impact of a repeated tape-strip challenge on skin barrier function following 4 weeks of twice-daily face and leg application of the investigational products and standard soap compared to the use of standard soap only.	Change from pre-challenge TEWL at Day 29 to the following time points: Removal of 3 tape strips (face) and 4 tape strips (legs); Removal of 6 tape strips (face) and 8 tape strips (legs); Removal of 9 tape strips (face) and 12 tape strips (legs). (Face: area 3 compared to area 4; leg: area 7 compared to area 8)
To evaluate the impact of a repeated tape-strip challenge on skin barrier integrity following 4 weeks of twice-daily face and leg application of the investigational products and standard soap compared to the use of standard soap only.	Total protein content extracted from all tape-strips: (Face: area 3 compared to area 4; leg: area 7 compared to area 8)
Safety	
To evaluate local tolerance.	Frequency and severity of adverse events.

Protocol Number: 209638 Draft Clinical Protocol

Study Design

This is a randomized, evaluator-blind, single-centre, two treatment regimen (test product 1 and test product 2), controlled (standard cleanser soap use only), split-body (left and right; side of the face and lower legs), parallel group clinical study designed to evaluate the impact of 4-weeks of twice-daily topical application of two developmental moisturizing cream formulations on skin barrier function in healthy subjects with dry, sensitive skin on the face and lower legs.

The chosen application sites are the face and the lower legs. The legs will be designated right and left, and the face will be split to right or left side.

There will be two treatment regimens included in this study;

- Treatment Regimen 1 = Test Product 1 + Standard Soap
- Treatment Regimen 2 = Test Product 2 + Standard Soap

Instrumental measurements of skin barrier function (TEWL; using a Tewameter) and skin moisturization (using a Corneometer) will be performed at specified time points. These measurements have been included to objectively model skin barrier function and moisturization throughout the product use and regression periods of this study.

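### SAP 4.6.1 leaves the SOC and PT rows of the AE tables as counts of events with no denominator, and its skin/non-skin flag cannot produce the skin-or-eye displays it plans

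*SAP*

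**What the plan says.** The protocol's one safety objective is local tolerance, and its endpoint is "Frequency and severity of adverse events" (Protocol 1, repeated in Protocol 3 and SAP 1.2). SAP 4.6.2 adds no other safety variable. Protocol 12.2.8 asks for frequencies and percentages overall, by system organ class (SOC) and by preferred term (PT). It does not say whether the unit is subjects or events.

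SAP 4.6.1 fills in the content of the tables. Its sentence opens with the subjects who had any AE, as a count and a percentage, and for everything else the wording is: "total number of AEs, number and percentage of AEs within each SOC and PT will be displayed". Treatment-related tables are to be shown in three columns (product 1 with soap, product 2 with soap, soap alone). All other AE tables are by regimen.

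On classification, the same section says of the pre-lock AE review: "During this review stage, AEs will be further categorized as skin or non-skin". The outputs then listed include:

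- "Table of TEAEs by Skin or Eye/Non-Skin or Non-Eye and PT" (Table 14.3.1.1.2)
- "Table of treatment-related TEAEs by Skin or Eye/Non-Skin or Non-Eye and PT" (Table 14.3.1.2.2)
- "Listing of treatment-emergent AEs classified as skin or eye" (Listing 14.3.2.4)

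**The concern.** The content sentence uses two units. Subjects are counted for having any AE; AEs are counted within each SOC and PT. A percentage of events is not an incidence. It depends on how many other events happened to occur in the column, and a subject with repeated episodes counts each time. Repeats are plausible with application twice a day for four weeks.

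The overall any-AE row mixes unrelated illness with application-site reactions. A reader judging local tolerance will look at the PT rows and the skin-or-eye rows, and there no subject percentage is specified.

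The classification problem is separate. Under a two-level flag an eye reaction is non-skin, yet three outputs need it grouped with skin. The SAP does not say what makes an AE an eye event. Eye reactions are a foreseeable local effect here: the cream goes on half the face including the forehead, subjects are warned about eye contact (Protocol 4.3, 6.1, 6.2), and active ocular disease is an exclusion (Protocol 5.3).

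**Working it through.** The documents give no AE figure to reproduce. The check sets the text side by side and then shows, with assumed counts, what follows.

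**1. Unit and denominator in SAP 4.6.1**

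| Row | Unit stated | Denominator stated |
|---|---|---|
| At least one AE | subjects, n and % | none; subjects in the column is natural |
| Total | AEs, n | not applicable |
| Each SOC and PT | AEs, n and % | none |

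No rule says that a subject counts once per SOC or PT, or at the highest severity in the severity tables. SAP Table 5-1 does not mention the matter.

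**2. Column sizes.** Protocol 5.1 plans about 150 randomized. If allocation is equal (an assumption), that is 150/2 = 75 per regimen. Every subject has one soap-only side, so the soap-only column holds 75 + 75 = 150, and 150/75 = 2. On the planned completers it is 60 + 60 = 120 against 60, the same ratio.

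**3. Two regimens (assumed counts; total AEs assumed as denominator).** Take 75 subjects per regimen. Regimen 1 has 20 AEs, 10 of them erythema in 10 subjects. Regimen 2 has 4 AEs, 2 of them erythema in 2 subjects.

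- Share of AEs: 10/20 = 50%; 2/4 = 50%.
- Subject incidence: 10/75 = 13.3%; 2/75 = 2.7%.

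If the denominator were subjects in the column, these same counts (one event per subject) would give 13.3% and 2.7%. The unstated denominator decides what the table shows.

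**4. Repeated episodes (assumed counts).** A PT occurs in 3 of 60 subjects, in a column with 20 AEs.

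- Subject incidence: 3/60 = 5.0%.
- One event each: 3/20 = 15% of AEs; 3/60 = 5.0% as events over subjects.
- Three events each: 9/20 = 45% of AEs; 9/60 = 15% as events over subjects.

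A subject denominator alone therefore does not restore the incidence once subjects have repeats. The numerator must be subjects too.

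**5. Product column against soap-only column (assumed counts; total AEs assumed as denominator).** A PT occurs once in each of 6 subjects in both columns, and each column has 20 AEs.

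- Share of AEs: 6/20 = 30% in both.
- Subject incidence: 6/75 = 8.0% for the product; 6/150 = 4.0% for soap alone.

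**6. Flag against outputs.** The flag has two levels, skin and non-skin. The outputs need skin or eye against the rest. The flag alone does not separate eye events from other non-skin events, so it cannot build the first group. The second row label is also loose. Taken literally, an event that is non-skin or non-eye is any event not classed as both, which takes in skin-only and eye-only events. The evident meaning is neither skin nor eye.

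**The case against.** A reader might infer that the only safety endpoint is never shown as an incidence. The documents do not support that. The sentence opens with the number and percentage of subjects having an AE, and the endpoint is worded as frequency and severity. The gap is at SOC and PT level only.

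A reader might infer that eye reactions will be left out of the local-reaction rows. The titles of two tables and a listing say otherwise, and every AE is coded to SOC and PT, so eye events remain identifiable. They would be misplaced only if the outputs were programmed from the stated flag alone, against their own titles.

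A reader might infer that a safety signal would be hidden. That also goes too far. In the erythema example the table would still show 10 against 2 events and 20 against 4 in total, and Listing 16.2.7.1 gives every AE for all randomized subjects.

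Two further points have force. The sentence is compressed, and its closing phrase on SOC and PT could be meant to govern the subject counts as well. The layout is set by Attachment 1, an embedded list of displays that is not reproduced, so the shells may already be right. What still stands is that the text, followed as written, specifies events without a denominator and a flag that does not match its outputs.

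**Conclusion.** The SAP text mis-specifies the detailed display of the only safety endpoint. Subject incidence is not specified by SOC and PT, the denominator of the event percentage is missing, and such percentages do not compare risk across columns, least of all where the soap-only column is about twice as large. The classification step is inconsistent with three outputs in its own section.

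This rests on the literal reading of SAP 4.6.1. The size of any distortion cannot be derived from the documents; the 50%/50% and 30%/30% examples use assumed counts and assume total AEs as the denominator. No hypothesis test, success criterion or primary result is affected. It should be corrected before unblinding, as a matter of clear reporting.

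**What to change.** In SAP 4.6.1, state one rule for the overall row and for every SOC and PT row: show how many subjects had one or more such events, the percentage this makes of the safety-population subjects in that column, and the count of events. Add that a subject counts once per SOC and once per PT, at the highest severity in the severity tables.

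Change the pre-lock classification to skin, eye, or neither, and say how an AE is assigned to eye. Relabel the second row of Tables 14.3.1.1.2 and 14.3.1.2.2 as neither skin nor eye.

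If the shells in Attachment 1 already do this, bring the SAP text into line with them. The cost is wording and shell edits. No new data are needed, conduct and alpha are untouched, and the event counts are kept.
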